9. PRE-STUDY AND CONCOMITANT INTERVENTION/MEDICATION

Concomitant medications will be documented during screening and updated during the study.

Disallowed medications for this study include: See Section 3.3

Concomitant therapies that are disallowed include: See Section 3.3

10. DEVIATIONS FROM THE PROTOCOL

Investigator will notify study sponsor upon identification of a protocol deviation. Major protocol deviations must be reported to the sponsor within 24 hours after discovery of the protocol deviation. The Investigator will report deviations per IRB/IEC requirements. All deviations will be tracked, and corrective actions implemented as appropriate.

If it becomes necessary for the Investigator to implement a deviation in order to eliminate an immediate hazard to the trial subject, the Investigator may implement the deviation immediately without notification to the sponsor. Within 24 hours after the implemented deviation, the Investigator must notify and provide the rationale to the Sponsor and, as required, the IEC/IRB.

11. STUDY TERMINATION

The occurrence of one or more Unanticipated Serious Adverse Device Effect (USADE), or any SAE where the relationship to study agent cannot be ruled out, may result in stopping further dispensing of test article. In the event of a USADE or SAE, the Sponsor may unmask the treatment regimen for the subject(s) and will discuss this with the Investigator before any further subjects are enrolled.

The Sponsor will determine when a study will be stopped. The Principal Investigator always has the discretion to initiate stopping the study based on patient safety or if information indicates the study's results are compromised.

JJVC reserves the right to terminate the study at any time for any reason. Additionally, the IEC/IRB reserves the right to terminate the study if an unreasonable risk is determined. The study can be terminated by the Principal Investigator at the individual clinical site due to specific clinical observations, if in their opinion, after a discussion with JJVC, it is determined that it would be unwise to continue at the clinical site.

JJVC (and the IEC/IRB and DMC, if applicable) will evaluate all adverse events. If it is determined that an adverse event presents an unreasonable risk, the investigation, or that part of the investigation presenting the risk, will be terminated, as soon as possible.

Should the study be terminated (either prematurely or as scheduled), the Investigator will notify the IEC/IRB and Regulatory Authority as required by local regulatory requirements.

12. PROCEDURE FOR HANDLING PRODUCT QUALITY COMPLAINTS

A Product Quality Complaint (PQC) refers to any written, electronic, or oral communication that alleges deficiencies related to the identity, quality, durability, reliability, safety, effectiveness or performance of test articles after they have been released for clinical trial use.

Potential complaints may come from a variety of sources including but not limited to subjects, clinical research associates (CRA), clinical operations managers (COM), medical monitors, and site personnel, etc. The following are not considered product quality complaints:

- Subject satisfaction inquiries reported via “Subjective Questionnaires” and “Patient Reported Outcomes (PRO)”.
- Clinical test articles that are stored improperly or damaged after receipt at the investigational site.
- Lens replacements that occur due to drops/fall-outs.
- Damage deemed by clinicians or clinical staff to be caused by handling by the user, and not indicative of a quality deficiency (i.e. tears, rips, etc.), only in situations where there is no deficiency alleged by the subject.

Within 24 hours of site personnel becoming aware that a PQC has occurred, the PQC must be recorded in the EDC system, which will trigger an automatic email notification to the appropriate COM/CRA and Clinical QA representative. In cases where the EDC system in use is not configured to send automatic notifications or when an EDC system is not used, the COM/CRA is responsible for notifying Clinical QA upon discovery that a PQC has occurred.

Upon receipt of the EDC notification, the COM/CRA will contact the study site to collect additional information which will include:

- Date the complaint was received/recorded in the EDC System (Date of Sponsor Awareness)
- Who received the complaint
- Study number
- Clinical site information (contact name, site ID, telephone number)
- Lot number(s)
- Unique Subject Identifier(s)
- Indication of who first observed complaint (site personnel or subject)
- OD/OS indication, along with whether the lens was inserted
- Any related AE number if applicable
- Detailed complaint description (scheduled/unscheduled visit, wear time, symptoms, resolution of symptoms, etc.)
- Eye Care Provider objective (slit lamp) findings if applicable
- Confirmation of product availability for return (and tracking information, if available), or rationale if product is not available for return [REDACTED]
[REDACTED])

Once a complaint is received, it will be assessed by the COM, CRA, or trained site personnel to determine if it is an Adverse Event/Serious Adverse Event (AE/SAE). If the complaint results in an AE/SAE, the COM/CRA, or trained site personnel will follow Section 13 of this

protocol. If the AE/SAE was potentially the result of a product quality related deficiency, these procedures also applies and will be executed in parallel.

In some cases, a PQC form may be generated in EDC by the site in error. In this event, the PQC forms will be marked “Intentionally Left Blank” or “ILB”. Justification for ILB must be documented.

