13.2. Assessing Adverse Events

In conjunction with the medical monitor, the Investigator will evaluate adverse events to ensure the events are categorized correctly. Elements of categorization will include:

- Seriousness/Classifications (see definition in Section 13.1)
- Causality or Relatedness – i.e. the relationship between the test article, study treatment or study procedures and the adverse event (not related; doubtful; possible; probable; very likely - see definition in Section 13.2.1)
- Adverse Event Severity – Adverse event severity is used to assess the degree of intensity of the adverse event (mild; moderate; severe for all events - see definition in Section 13.2.2).
- Outcome – not Recovered or Not Resolved; Recovering or Resolving; Recovered or Resolved with Sequelae; Recovered or Resolved; Death Related to Adverse Event; Unknown
- Actions Taken – none; temporarily discontinued; permanently discontinued; other

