13.3. Documentation and Follow-Up of Adverse Events

The recording and documenting of adverse events (ocular and non-ocular) begins when the subjects are exposed to the test article, study treatment or study procedure. Adverse events reported before the use of test article, start of study treatment, or study procedures will be recorded as medical history. However, if the condition deteriorates at any time during the study it will be recorded and reported as an AE. Untoward medical events reported after the subject's exit from the study will be recorded as adverse events at the discretion of the Investigator.

Upon finding an adverse event, the Principal Investigator will document the condition in the subject record and in the eCRFs. He/she will complete the Adverse Event /eCRF.

Complete descriptions of all adverse events must be available in the subject record. All Adverse Events including local and systemic reactions not meeting the criteria for "serious adverse events" shall be captured on the appropriate case report form or electronic data system. All adverse events occurring while the subject is enrolled in the study must be documented appropriately regardless of relationship.

It is the Investigator's responsibility to maintain documentation of each reported adverse event. All adverse events will be followed in accordance with applicable licensing requirements. Such documentation will include the following:

- Adverse event (diagnosis not symptom)
- Drawings or photographs (where appropriate) that detail the finding (e.g., size, location, and depth, etc.)
- Date the clinical site was notified
- Date and time of onset
- Date and time of resolution

- Adverse event classification, severity, and relationship to test articles, as applicable
- Treatment regimen instituted, including concomitant medications prescribed, in accordance with applicable licensing requirements
- Any referral to another health care provider if needed
- Outcome, ocular damage (if any)
- Likely etiology
- Best corrected visual acuity at the discovery of the event and upon conclusion of the event

In addition, if an infiltrate(s) is present, he/she will complete the Corneal Infiltrate Assessment /eCRF. Where necessary, a culture of the corneal lesion will be collected to determine if the infection is microbial in nature. If cultures are collected, the date of culture collection and laboratory utilized will be recorded.

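### Protocol section 12 lets a COM, CRA or trained site staff member decide whether a complaint is an AE/SAE without the Investigator, and this is not reconciled with section 13.2

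*Protocol*

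**What the plan says.** Protocol section 12 sets out how a product quality complaint is handled. After the complaint is entered, "Upon receipt of the EDC notification, the COM/CRA will contact the study site to collect additional information which will include" a list of items. One is "Detailed complaint description (scheduled/unscheduled visit, wear time, symptoms, resolution of symptoms, etc"), and others are slit lamp findings where applicable and "Any related AE number if applicable". On the safety question, "it will be assessed by the COM, CRA, or trained site personnel to determine if it is an Adverse Event/Serious Adverse Event (AE/SAE"). The next sentence deals with a positive answer: "If the complaint results in an AE/SAE, the COM/CRA, or trained site personnel will follow Section 13". Nothing is said about a negative one.

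Section 13.2 allocates the work on adverse events differently: "In conjunction with the medical monitor, the Investigator will evaluate adverse events to ensure the events are categorized correctly". The first element of that categorization is "Seriousness/Classifications (see definition in Section 13.1"). Section 13.2.1 has the investigator judge causality. Section 13.3 adds: "Upon finding an adverse event, the Principal Investigator will document the condition in the subject record and in the eCRFs".

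**The concern.** A complaint can be a quality problem and an adverse event at once. Section 12 defines complaints to include alleged deficiencies in safety, and the details collected include symptoms and slit lamp findings. Deciding whether such a complaint is an adverse event, and whether it is serious, is a clinical judgement. Section 12 allows it to be made by a Clinical Operations Manager (COM) or Clinical Research Associate (CRA) alone.

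The decision has consequences. Sections 13.4 and 13.4.1 require serious or significant events to reach the Sponsor within 24 hours of discovery. SAE status also feeds the provision on stopping further dispensing, in the synopsis and in section 11. According to section 1, lenses from the new manufacturing line are being clinically evaluated for the first time in this study, so complaints that are both quality and safety matters are the ones the study should handle most carefully.

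**Working it through.** There is no figure to reproduce and no arithmetic to do. The check is a comparison of the passages.

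1. **Who decides under section 12.** Three alternatives are joined by *or*: COM, CRA, trained site personnel. Any one suffices. The Investigator and medical monitor are not named.

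2. **What follows the decision.** A yes leads into section 13. For a no, section 12 requires neither a record of the reasoning nor Investigator review. By contrast, the same section does require a documented justification when a complaint form was opened in error.

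3. **Who decides under section 13.** Evaluation and categorization, with seriousness as one element, belong to the Investigator with the medical monitor (13.2). Causality (13.2.1) and documentation (13.3) belong to the investigator side as well, and section 15.2 has the Investigator review and initial adverse event notes. The SAE definition in 13.1 relies on medical judgement for important medical events that do not meet the other criteria.

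4. **Where the sections meet.** There are two separate parts:
   - *Seriousness.* Section 12's determination covers SAE status, and 13.2 lists seriousness among the elements it allocates. This is the same judgement given to different people, so it is a direct overlap.
   - *Whether there is an event at all.* Section 13.2 starts from events already identified as adverse events, so section 12 does not contradict it here. The result is a gap: a complaint judged negative need not be seen by the Investigator through this procedure.

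5. **Whether such complaints can be clinical.** Section 13.1 lists superficial punctate keratitis and localized allergic reactions as adverse events. Either could first appear as a complaint about the lens, and both need a clinician to recognise them.

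6. **What else would catch the event.** Visits 2, 3 and 4 each include adverse event review, an open-ended symptom question and slit lamp grading (section 7.2). Unscheduled visits include adverse event review and slit lamp findings (7.3). Section 13.3 requires every adverse event during enrolment to be documented. Follow-up visits come 13 to 15 days after each dispensing, whereas the serious/significant reporting limit is 24 hours. A routine visit can therefore recover a missed event but may not do so within the reporting limit. The exposure is the interval between visits.

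7. **What reaches the analysis.** SAP section 12.1 plans listings of reported adverse events, with no rate and no comparison. The primary safety endpoints, slit lamp findings and lens fit, come from examinations at study visits and do not pass through the complaint procedure.

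**The case against.** The strongest defence is that section 12 describes triage only. Positives go straight to section 13, where the Investigator categorizes them, judges causality and documents them. Site staff are an equal alternative to the COM and CRA, an adverse event may already have its own number when the complaint is processed, and section 11 gives the sponsor a role in evaluating all adverse events. The Investigator's section 13 duties also continue whatever a COM or CRA decides.

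Most of this stands, and it keeps the point small. It does not cover the complaint judged negative, and it does not explain why SAE status is decided under section 12 when 13.2 gives seriousness to someone else. The sponsor's role in section 11 concerns events already identified as adverse events.

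Four stronger readings are tempting, and the documents do not support them:

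- **Unmasking.** The COM and CRA collect lot numbers, so a reader might infer that unmasked staff screen out Test-lens events. Only subjects are masked, and only to the Control lens (5.2). No assessor masking is claimed, and the Investigator or designee already reads the assignment from the randomization scheme (5.3).
- **Built-in delay.** The order of paragraphs might suggest that the decision waits for complaint entry and information gathering. The text ties assessment to receipt of the complaint, and the 24-hour limit still runs from discovery.
- **A negative decision closes the safety path.** It does not, given the other routes in sections 7.2, 7.3 and 13.3.
- **Decision reserved to sponsor staff.** Site personnel are named too, and the protocol does not state who employs the COM and CRA.

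**Conclusion.** The point holds as an unreconciled allocation of responsibility. Section 12 permits an AE/SAE determination without the Investigator or medical monitor and without Investigator review of a negative answer, while 13.2 gives evaluation, including seriousness, to those two roles. The passages must be reconciled.

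It is a minor, worthwhile correction. Its reach is complaints handled between visits, and its relevance is to timely safety reporting and the stopping provision. Sample size, error rates and the primary analyses are unaffected. A reader might want to express the risk as a share of adverse events lost. The documents give no complaint counts and no expected adverse event rate, and the SAP plans no rate that such a figure would correspond to, so none is offered.

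The conclusion assumes that trained site personnel in section 12 does not mean the Investigator exclusively. Even if the term includes the Investigator, the *or* still lets the COM or CRA decide alone.

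**What to change.** Replace the determination sentence in section 12 with:

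> Any complaint, including one first received by the COM, CRA or medical monitor, is passed to the Investigator on receipt; the Investigator determines under Section 13.2 whether it is an AE/SAE, and the COM/CRA confirm that this determination is on file.

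The clause on first receipt is needed because section 12 lists COMs, CRAs and medical monitors among the sources of complaints, so a rule that starts only when the site becomes aware would miss those. The hand-over to section 13 for positive determinations can stay as it is.

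The cost is one protocol sentence and slightly more Investigator review of complaints. Section 13.2 already gives the Investigator and medical monitor this role, so no new role is created. No SAP change is needed.

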13. ADVERSE EVENTS

13.1. Definitions and Classifications

Adverse Event (AE) – An AE is “any untoward medical occurrence, unintended disease or injury, or untoward clinical signs (including abnormal laboratory findings) in subjects, users or other persons, whether or not related to the investigational medical device.

Note 1 to entry: This definition includes events related to the investigational medical device or the comparator.

Note 2 to entry: This definition includes events related to the procedures involved.

Note 3 to entry: For users or other persons, this definition is restricted to events related to investigational medical devices.”¹

An AE includes any condition (including a pre-existing condition) that:

1. Was not present prior to the study, but appeared or reappeared following initiation of the study
2. Was present prior to the study but worsened during the study. This would include any condition resulting from concomitant illnesses, reactions to concomitant medications, or progression of disease states
3. Pregnancy must be documented as an adverse event and must be reported to the clinical monitor and to the Sponsor immediately upon learning of the event

Serious Adverse Event (SAE) – An SAE is any untoward medical occurrence that:

- Results in death
- Is life threatening
- Requires in-patient hospitalization or prolongation of existing hospitalization
- Results in persistent or significant disability/incapacity (e.g., a sight threatening event, a significant persistent or permanent change, impairment, damage, or disruption to the subject’s body)
- Is a congenital anomaly/birth defect
- Requires intervention to prevent permanent damage (the use of the test article resulting in a condition which requires medical or surgical intervention to preclude permanent impairment of the body structure or a body function). Important medical events that may not result in death, be life-threatening, or require hospitalization may be considered an SAE when, based upon appropriate medical judgment, they may jeopardize the patient or subject and may require medical or surgical intervention to prevent one of the outcomes listed in the above definition.

Diagnoses and conditions that are considered Ocular Serious Adverse Events include, but not limited to:

- Microbial Keratitis (MK)
- Iritis (including cells in the anterior chamber)
- Permanent decrease in best spectacle corrected visual acuity equivalent to 2 acuity lines or greater
- Central Corneal Opacity
- Central Corneal Neovascularization
- Uveitis
- Endophthalmitis
- Hypopyon
- Hyphemia
- Penetration of Bowman's Membrane
- Persistent Epithelial Defect
- Limbal cell Damage leading to Conjunctivalization

Significant Adverse Events – Those events that are usually symptomatic and warrant discontinuation (temporary or permanent) of the test article (excluding Serious Adverse Events).

Diagnoses and conditions that are considered Ocular Significant Adverse Events include, but not limited to the following:

- Contact Lens Induced Peripheral Ulcer (CLPU)
- Significant Infiltrative Events (SIE)
- Superior Epithelial Arcuate Lesions (SEALS)
- Any Temporary Loss of >2 Lines of BSCVA
- Other Grade 3 or higher corneal findings, such as abrasions or edema
- Non-contact lens related corneal events - e.g. Epidemic Keratoconjunctivitis (EKC)
- Asymptomatic Corneal Scar
- Any corneal event which necessitates temporary lens discontinuation >2 weeks

Non-Significant Adverse Events – Those conditions that are usually asymptomatic and usually do not warrant discontinuation (temporary or permanent) of the test article. However, the Investigator may choose to treat as a precautionary measure.

Diagnoses and conditions that are considered Ocular Non-Significant Adverse Events include, but not limited to the following:

- Non-significant Infiltrative Event (NSIE)
- Contact Lens Papillary Conjunctivitis (CLPC)
- Superficial Punctate Keratitis (SPK)
- Conjunctivitis: Bacterial, Viral, Allergic
- Blepharitis
- Meibomianitis
- Contact Dermatitis
- Localized Allergic Reactions

- Any corneal event not explicitly defined as serious or significant adverse event, which necessitates temporary lens discontinuation < 2 weeks

Adverse Device Effect (ADE) – An ADE is an “adverse event related to the use of an investigational medical device.

Note 1 to entry: This definition includes adverse events resulting from insufficient or inadequate instructions for use, deployment, implantation, installation, or operation, or any malfunction of the investigational medical device.

Note 2 to entry: This definition includes any event resulting from use error or from intentional misuse of the investigational medical device.”¹

Unanticipated Adverse Device Effect (UADE) – Any serious adverse effect on health or safety or any life-threatening problem or death caused by, or associated with, the test article, if that effect, problem, or death was not previously identified in nature, severity, or degree of incidence in the investigational plan, Investigator’s Brochure or protocol, or any other unanticipated serious problem associated with the test article that relates to the rights, safety and welfare of subjects.

13.2. Assessing Adverse Events

In conjunction with the medical monitor, the Investigator will evaluate adverse events to ensure the events are categorized correctly. Elements of categorization will include:

- Seriousness/Classifications (see definition in Section 13.1)
- Causality or Relatedness – i.e. the relationship between the test article, study treatment or study procedures and the adverse event (not related; doubtful; possible; probable; very likely - see definition in Section 13.2.1)
- Adverse Event Severity – Adverse event severity is used to assess the degree of intensity of the adverse event (mild; moderate; severe for all events - see definition in Section 13.2.2).
- Outcome – not Recovered or Not Resolved; Recovering or Resolving; Recovered or Resolved with Sequelae; Recovered or Resolved; Death Related to Adverse Event; Unknown
- Actions Taken – none; temporarily discontinued; permanently discontinued; other

13.2.1 Causality Assessment

Causality Assessment – A determination of the relationship between an adverse event and the test article. The test article relationship for each adverse event should be determined by the investigator using these explanations:

- Not Related- An adverse event that is not related to the use of the test article, study treatment or study procedures.
- Unlikely Related – An adverse event for which an alternative explanation is more likely, e.g. concomitant treatment, concomitant disease(s), or the relationship of time suggests that a causal relationship is not likely.
- Possibly Related – An adverse event that might be due to the use of the test article, or to the study treatment or study procedures. An alternative explanation, e.g. concomitant

treatment, concomitant disease(s), is inconclusive. The relationship in time is reasonable. Therefore, the causal relationship cannot be excluded.

- Related – An adverse event that is listed as a possible adverse effect (device) or adverse reaction (drug) and cannot be reasonably explained by an alternative explanation, e.g. concomitant treatment of concomitant disease(s). The relationship in time is very suggestive, e.g. it is confirmed by de-challenge and re-challenge.

